4.2.2.2 Stopping Rules in Individual Participants for Other Circumstances

Any participant that experiences any of the following after first study vaccination will not receive further injections of study vaccine:

- Withdrawal of consent
- Pregnancy
- Any clinically significant medical condition that, in the opinion of the Investigator or the blinded SRC, poses an additional risk to the participant if he/she continues to participate in the study.

4.2.3 Withdrawal of Participant From Study

Participants are free to withdraw from participation in the study at any time upon request, without any consequence.

A participant will be withdrawn from the study if any of the following occur prior to first administration of study vaccine:

- The participant requests to discontinue study participation.
- Study vaccine is not administered.

A participant may withdraw from the study at any time at his/her own request. Reasons for discontinuation from the study may include the following:

- Refused further follow-up
- Lost to follow-up
- Death

- Study terminated by the Sponsor
- Participant request
- Investigator request
- Protocol deviation
- Opportunity to receive an approved COVID-19 vaccine

For any participant terminating the study sooner than 60 days after last study vaccine administration, the following guidelines should be observed:

- The participant should also be reminded about use of highly effective contraception until 60 days following last study vaccine exposure.
- Any pregnancy occurring this window should be reported to the Sponsor as soon as feasible.
- Should the Principal Investigator (PI)/site become aware at any time of any death or pregnancy occurring in these participants it should be reported to Sponsor.

The following guidance applies for participants who choose to exit the study to receive approved COVID-19 vaccine (Note: Participants can continue to be followed for safety even if they receive an authorized COVID-19 vaccine.):

- The participant is advised to wait 4 weeks since the last study vaccination before seeking licensed vaccine.
- Should the former participant experience any severe or serious or concerning AEs following receipt of the approved COVID-19 vaccine, they should notify the site. These events would be collected as post-study AEs. The participant should also report these AEs to the vaccine provider.

The Investigator must capture the reason for withdrawal in the electronic Case Report Form (eCRF) for all participants.

If a participant withdraws from the study, he/she may request destruction of any remaining samples taken and not tested, and the Investigator must document any such requests in the site study records and notify the Sponsor or CRO accordingly.

If a participant withdraws consent and specifies no further contact with him/her or persons previously authorized by the participant to provide this information, this should be documented by the Investigator in the study source documents. In the event that vital status (whether the participant is alive or dead) is evaluated, publicly available information should be used to determine vital status only as appropriately directed in accordance with local law.

4.2.4 Study-Wide Pausing and Stopping Rules

If any of the following is observed in the study, further administration of study vaccine to all participants will be paused until the blinded SRC has reviewed all relevant safety data and determined that it is safe for dosing with study vaccine to resume. Termination of the study will depend on evaluation of these safety data and the findings of the SRC.

- Any SAE considered possibly, probably, or definitely related to study vaccine administration (as confirmed by SRC review)
- Any anaphylactic AE following study vaccine administration

- Any clinically apparent hypersensitivity episode that is considered at least moderate in severity, is considered probably or definitely related to study vaccine administration (as confirmed by SRC review), and has the following features:
 - Is not confined to the injection site
 - Is immediate in onset (within ≤ 4 hours after vaccination) or, if delayed, involves more than 1 organ system
- Any suspected or confirmed myocarditis, pericarditis, and/or myopericarditis event that is considered by the investigator to be possibly, probably, or definitely related to study vaccine administration or is temporally associated (within 6 weeks) with vaccine administration.
- Any death due to SARS-CoV-2 infection or any severe (per the Food and Drug Administration [FDA] criteria [[Appendix 7](#)]) SARS-CoV-2 infection in a vaccinated participant.

Events meeting Pausing Rule definitions will be referred to the SRC (which will remain blinded to the vaccine assignment), where the case details and the assessment of the event causality will be assessed. Should the SRC confirm that a Pausing Rule was met, Investigators will be immediately instructed to pause dosing, and the applicable health authorities will be notified within 1 business day of determination that a Pausing Rule has been met.

Study vaccine administrations will continue to be paused while the case undergoes review. If review of the event(s) leads to SRC recommendation for an unblinded data review, a designated medical team (separate from the study team overseeing the study) from the Sponsor and including an independent medical reviewer will convene to review the unblinded details. After evaluation of these relevant data, this separate safety review team will make a recommendation to the SRC. The SRC will then document the decision of whether the study should be discontinued, should be modified prior to resumption of study vaccine administrations, or should continue without protocol modification. This recommendation will be provided to Health Authorities and Investigators prior to resumption of study procedures (if applicable).

Should the study dosing pause or stop altogether, participants will continue clinic visits for safety assessments only through the Final Visit, as described in the Schedule of Assessments.

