Myocarditis and Pericarditis	
 Participants are to be instructed to seek medical attention and notify study staff immediately should symptoms of myocarditis and /or pericarditis occur post-vaccination including chest pain, shortness of breath, or feelings of a fast-beating, fluttering or pounding heart. An unscheduled visit should be performed if feasible for further follow-up and investigation of potential myocarditis or pericarditis. Participants reporting acute chest pain, shortness of breath, palpitations, or other signs of myocarditis or pericarditis within 6 weeks after vaccination must be referred to a cardiologist for evaluation and management. Cases of myocarditis and/or pericarditis will be followed until resolution of symptoms and abnormal test findings. Individuals with a history of myocarditis, pericarditis or cardiomyopathy will be excluded from study participation. A targeted questionnaire will be utilized to conduct follow-up for potential cases of myocarditis and/or pericarditis. Participants with a reported AE/SAE of myocarditis and/or pericarditis after study vaccine administration will be excluded from receiving further doses of study vaccine. Pericarditis and/or myocarditis are considered AESIs and are thus subject to expedited reporting requirements. The investigator must notify the Sponsor within 24 hours of knowledge of any events. A single myocarditis or pericarditis event considered to be related to study vaccination will result in a study pause according to study stopping rules. 
Note: Myocarditis and/or pericarditis has not been observed with ARCT-021, ARCT-154 or ARCT-165, but has been observed with other mRNA SARS-CoV-2 vaccines.

Hypertension	
 Vital signs including blood pressure measurements are to be performed at multiple study visits including prior and following each study vaccine administration including at Days 4, 8 and 15 following any study vaccine administration to identify any clinically significant abnormalities or elevations in blood pressure. Participants with a reported AE/SAE of hypertensive crisis after study vaccine administration will be excluded from receiving further doses of study vaccine.

Table 1 Risk Minimization Measures Included in Clinical Studies of ARCT-021, ARCT-154, and ARCT-165

Risk	Mitigation
------	------------

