4.2.2 Discontinuation of Study Vaccine (Participant)

4.2.2.1 Stopping Rules for Adverse Events in Individual Participants

A participant must not receive further study vaccine administrations if they experience any of the following AEs:

- Grade 3 solicited AEs (as confirmed by a blinded SRC review)
- Any anaphylactic reaction
- Severe related (possibly, probably, or definitely) unsolicited AEs
- Any clinically apparent hypersensitivity episode that is considered at least moderate in severity, is considered possibly, probably, or definitely related to study vaccine administration (as assessed by the Investigator and review of the SRC) and has the following features:
 - is not confined to the injection site
 - is immediate in onset (within ≤ 4 hours after vaccination) OR if delayed, involves more than one organ system
- Any serious adverse event (SAE) judged to be related (possibly, probably, or definitely) to study vaccine.
- Myocarditis and/or pericarditis
- Hypertensive crisis

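### Protocol 4.2.4 gives two starting points for the study-wide dosing pause, leaving anaphylaxis and myocarditis/pericarditis open to two readings

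*Protocol*

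**What the plan says.** Protocol 4.2.4 opens with a rule tied to observation. If any listed event occurs, "further administration of study vaccine to all participants will be paused until the blinded SRC has reviewed all relevant safety data" and has found it safe to resume. Five triggers follow. Related SAEs and hypersensitivity each carry a parenthesis that makes SRC confirmation part of the trigger. Anaphylaxis does not: "Any anaphylactic AE following study vaccine administration". Nor does the myocarditis/pericarditis/myopericarditis trigger. It covers suspected as well as confirmed cases and applies to an "event that is considered by the investigator to be possibly, probably, or definitely related to study vaccine administration or is temporally associated" with vaccination, defined as within 6 weeks. The fifth trigger is death due to SARS-CoV-2 infection, or severe infection by the FDA criteria.

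The closing paragraph describes what happens next. "Events meeting Pausing Rule definitions will be referred to the SRC", which assesses the case and its causality. Then: "Should the SRC confirm that a Pausing Rule was met, Investigators will be immediately instructed to pause dosing". Health authorities are told within 1 business day of that determination. The next paragraph adds: "Study vaccine administrations will continue to be paused while the case undergoes review".

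Three other places bear on the point:
- Table 1 in 1.7.1: "A single myocarditis or pericarditis event considered to be related to study vaccination will result in a study pause according to study stopping rules".
- Section 7.6.1 gives the SRC the task of confirming that a rule was met. It does not say whether dosing is held meanwhile.
- Section 4.2.2.1 protects the affected participant: "A participant must not receive further study vaccine administrations if they experience any of the following AEs". Its list includes anaphylactic reactions, myocarditis and pericarditis.

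**The concern.** A study-wide pause protects the other participants, so its starting point is the substance of the rule. Under the opening sentence the pause begins when the event is observed. Under the closing paragraph an event that already meets a definition goes to the SRC, and Investigators are told to pause after the SRC agrees. After an anaphylactic reaction or a suspected myocarditis, a site following the opening sentence would hold, while a site waiting for the instruction could go on dosing.

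There is also a practical gap. The study may run in up to three countries (Protocol 3.1), and the SAP (4.8.1.4) expects approximately 4 sites. A site that did not see the event cannot act on it until told, and the instruction that 4.2.4 describes comes after SRC confirmation.

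**Working it through.** There is no plan figure to reproduce. The check compares wording and adds one piece of date arithmetic.

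**Step 1. Does each trigger in 4.2.4 depend on the SRC?**

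| Trigger | SRC part of the trigger? | Can the two starts be reconciled? |
|---|---|---|
| Related SAE | Yes, in the trigger's wording | Yes: the trigger is not complete until the SRC confirms |
| Anaphylactic AE | No | No |
| Hypersensitivity | Yes, in the trigger's wording | Yes, as for SAEs |
| Myocarditis/pericarditis/myopericarditis | No: investigator judgement or timing is enough | No |
| COVID-19 death or severe infection | Not in the trigger's wording, but see below | Death limb arguable; severe limb not claimed |

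On the last row, attributing a death to the infection needs a judgement, and Appendix 7 lists death among the criteria for a severe case. Protocol 6.3.1.2.15 has the Sponsor or designee review cases for severity, and SAP 3.4.3 places the severity assessment in SRC meetings.

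Count: 2 affected + 1 arguable + 2 reconcilable = 5.

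**Step 2. Does other text fix the start?**
- The statement that dosing continues to be paused follows the confirmation sentence. It fits a pause already in force, but also a pause just ordered.
- Table 1 mentions no SRC step, but it defers to the stopping rules, which are the text in question.
- Section 7.6.1 repeats the confirmation role and is silent on dosing before it.

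**Step 3. Which time limits are stated?**
- Site to Sponsor for AESIs: 24 hours (6.3.1.2.5).
- Site to CRO for SAEs: 24 hours (6.3.1.2.12).
- SRC confirmation: none stated.
- Health authorities: 1 business day, counted from the determination (4.2.4).

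The interval between the site's report and the instruction to pause therefore has no stated upper limit.

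**Step 4. Is the SRC needed to establish the myocarditis/pericarditis trigger?**
- Temporal limb: 6 × 7 = 42 days.
- Interval between Cohort A doses: 29 − 1 = 28 days, or 29 days using the +1 day window in Appendix 1.
- Margin: 42 − 28 = 14 days, or 42 − 29 = 13 days.

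Any onset between the two Cohort A doses meets the trigger on timing alone, so no causality finding is needed. This shows that the trigger can be complete before the SRC acts. It does not show when the pause starts.

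**The case against.** The strongest reply is that the two sentences do not contradict each other. The opening sentence is a mandatory requirement that Investigators must follow. The closing sentence does not make confirmation a precondition in terms, and it is paired with notice to health authorities, so it can be read as formal notification of a hold already begun. The continuing-pause wording fits that reading, and Table 1 describes a pause with no SRC step. This largely stands: an immediate hold is the probable intent. But the text does not say that the later instruction merely formalises an existing hold, and an instruction to pause normally implies that dosing has not yet been paused.

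A second reply is that the practical reach is small. The plan is for about 72 participants. The SRC includes each site's principal investigator, as applicable, so a member would learn of the event at referral. Remaining participants are dosed only after SRC review of 3 days of sentinel data, and the SRC recommends whether second dosing in Cohort A proceeds. Cohort B receives one dose, and preliminary Cohort B data are already cited, so much of its dosing was probably done (an inference). These features reduce exposure but do not close the gap. Learning of an event is not an instruction to hold. Sentinel review happens once. The second-dose recommendation does not cover first doses, and the text does not say whether it is given once or repeatedly.

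Two stronger readings are tempting. A reader might infer that the protocol authorises dosing after anaphylaxis until the SRC confirms. No sentence says so, and the opening sentence points the other way. A reader might also infer that all five triggers are affected, or that every possible event should bring an immediate hold. Two triggers deliberately include SRC confirmation; removing it would be a design trade-off, not the correction of an error.

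**Conclusion.** Wrong as written, limited to the inconsistent start of the pause. The probable intent is an immediate hold, so this is an inconsistency with a likely intended meaning rather than a flat contradiction. It should still be fixed, because two sites acting in good faith could apply a stated safety rule differently.

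Its size is two of five triggers, with COVID-19 death arguable. No endpoint, analysis population definition, planned method or statistical figure changes. The number of doses that might be given before an instruction arrives cannot be estimated from the documents. The conclusion assumes that a site could reasonably treat the post-confirmation instruction as the start of the pause; confidence is medium for that reason.

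**What to change.** Revise the closing paragraph of 4.2.4, and align 7.6.1, along these lines: for any anaphylactic AE, and for suspected or confirmed myocarditis, pericarditis or myopericarditis that meets the existing trigger, dosing of all participants is held and all sites are notified as soon as the event is observed or reported; the SRC then confirms whether the rule was met and decides whether dosing may resume.

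Leave the two SRC-confirmed triggers as they are. Add that an event meeting more than one trigger takes the earliest start. This is needed because 6.3.1.2.5 treats myocarditis or pericarditis in temporal association with vaccination as potentially related and serious, so the same event can also fall under the related-SAE trigger.

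The cost is an amendment submitted to the IRB/IEC (11.2.1), a site notice, and occasional short holds for events that the SRC later finds did not meet a rule. A hold could push a Day 29 dose past its +1 day window. If that is the dosing window meant in the immunogenicity set definition (Protocol 7.2, SAP 4.2), which is an assumption, the participant could drop out of that set.

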2 STUDY OBJECTIVES AND ENDPOINTS

2.1 Primary Objectives and Endpoints

The primary objective(s) and endpoints are presented in [Table 2](#).

Table 2 Primary Objectives and Endpoints

Primary Objectives	Endpoint Description
1. To describe the safety and reactogenicity of 3 investigational SARS-CoV-2 self-amplifying RNA vaccines	
Endpoint 1: Safety will be summarized for each vaccination as the number and percentage of participants with the following:
 
d. Any solicited local or systemic AE collected for 7 days after each study vaccination, which will be assessed by toxicity gradee. Any unsolicited AE collected for 28 days after each study vaccination, which will be assessed by severity and relationship to study vaccinef. Any MAAEs, AEs leading to discontinuation from study vaccine/study withdrawal, or SAEs through Final Visit/ET Visit (Final Visit is defined as 365 days after the last study vaccine dose)
2. To describe the immunogenicity (antibody responses) of 3 investigational SARS-CoV-2 self-amplifying RNA vaccines	
Immunogenicity (antibody responses) will be evaluated after vaccination using the following assays and approaches:
 
Endpoint 2: SARS-CoV-2 neutralizing antibody concentrations by pseudoviral microneutralization assay (ancestral strain, D614G variant, and SARS-CoV-2 Beta variant [as available]). Assay results will be evaluated as follows:
 
a. GMCs at each time point designated in the Schedule of Assessments (Appendix 1 and Appendix 2).b. GMFR from before vaccination to each subsequent time point evaluated after vaccination.c. Proportion of participants achieving ≥ 4-fold rise from before vaccination to each subsequent time point evaluated after vaccination.d. GMC ratio (ARCT-021/ARCT-165, ARCT-165/ARCT-154, and ARCT-021/ARCT-154) measured at all time points evaluated.e. Exploratory: Neutralizing antibody responses to other SARS-CoV-2 variant strains may also be performed and will be described in the SAP. 
Endpoint 3: Binding antibody concentration: IgG to variant-specific SARS-CoV-2 full-length spike, RBD, and N antigens measured by MSD multiplex assay

Table 2 Primary Objectives and Endpoints

Primary Objectives	Endpoint Description

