7.5.4 Immunogenicity Analyses

Analyses will be conducted using the Immunogenicity set as defined for the specific assay under evaluation. Immunogenicity endpoints are described in Section 2 and will be summarized, by study vaccine group and time point, using descriptive statistics. If formal statistical testing is performed, it will be described in the SAP.

The kinetics of immune response following vaccination with each study vaccination will be evaluated in binding, neutralizing antibody responses, and CMI through 365 days after the last vaccination.

Participants who have a nucleocapsid (N) binding antibody test that is positive during the study will be identified, and sensitivity analyses of the immunogenicity data will be conducted with and without participants with this positive test.

A full description of planned analyses for immunogenicity endpoints will be contained in the SAP prior to the time of the intended analysis.

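### As written, any dosing pause puts every participant on safety-only visits through the Final Visit, including those already fully dosed, which conflicts with Primary Objective 2 and the sampling schedule

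*Protocol*

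**What the plan says.** Under Protocol section 4.2.4, when a listed event is observed, "further administration of study vaccine to all participants will be paused until the blinded SRC has reviewed all relevant safety data". A single event is enough; one of the listed triggers is "Any SAE considered possibly, probably, or definitely related to study vaccine administration (as confirmed by SRC review"). Sites are told to pause once the SRC confirms that a rule was met.

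The pause may be lifted. The SRC can decide that the study should be discontinued, that it "should be modified prior to resumption of study vaccine administrations, or should continue without protocol modification". The text adds: "This recommendation will be provided to Health Authorities and Investigators prior to resumption of study procedures (if applicable").

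The section closes with the sentence at issue: "Should the study dosing pause or stop altogether, participants will continue clinic visits for safety assessments only through the Final Visit". It ends by referring the reader to the Schedule of Assessments.

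Three other parts of the Protocol bear on this:

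- Primary Objective 2 (section 2.1, Table 2) is "To describe the immunogenicity (antibody responses) of 3 investigational SARS-CoV-2 self-amplifying RNA vaccines", with endpoints that include "GMCs at each time point designated in the Schedule of Assessments".
- Section 7.5.4 says that the kinetics of the response "will be evaluated in binding, neutralizing antibody responses, and CMI through 365 days after the last vaccination".
- Appendices 1 and 2 schedule antibody blood through Day 394 (Cohort A) and Day 366 (Cohort B), with T-cell blood at a subset of those visits.

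**The concern.** The closing sentence of section 4.2.4 names both a pause and a stop, refers to participants without qualification, restricts visits to safety, and runs to the Final Visit and not to the end of the pause. It makes no distinction between participants still awaiting a dose and those who have completed their assigned doses. Neither document states elsewhere that immunogenicity sampling continues.

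Cohort B shows the difficulty. These participants are fully dosed from Day 1, so a dosing pause changes nothing in their treatment. Their follow-up can nonetheless overlap dosing in Sub-cohort A2. Protocol version 1.0 is dated 27 May 2021, so no Cohort B participant could reach Day 366 before 27 May 2022, and Sub-cohort A2 was introduced in version 3.0, dated 10 March 2022. An event in Sub-cohort A2 could therefore, on the literal wording, halt antibody sampling in Cohort B participants who still come to every visit.

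What is at stake is sampling for one of the two primary objectives and for the exploratory CMI objective. A sample not drawn on its day is gone. Missing data are not imputed (Protocol 7.5.5, SAP 4.8.1.2), and the SAP has no rule for samples missed because of a pause.

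**Working it through.** The plan gives no figure to reproduce: Protocol 7.1 states that no formal sample size calculation was done, and no trigger rate is given. The check is a comparison of texts, a count of draws, and an illustration of how often a trigger might occur.

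**1. Texts side by side**

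| Question | Closing sentence of 4.2.4 | Other text |
|---|---|---|
| Does it apply to a temporary pause? | Yes, pause and stop are both named | 4.2.4 elsewhere: a pause lasts until SRC review and the study may continue unmodified |
| When does it end? | At the Final Visit | 4.2.4 elsewhere: procedures may resume, if applicable |
| Are fully dosed participants exempt? | No exemption | Cohort B has a single dose on Day 1 |
| Is antibody blood drawn? | Safety assessments only | Table 2, section 7.5.4 and Appendices 1 and 2: drawn at each designated time point |
| Which schedule governs? | The Schedule of Assessments | Appendices 1 and 2 have no safety-only version and list the draws |

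The sentence cannot be followed together with the objectives and the appendices. The resumption text narrows the conflict without removing it, because it does not mention sampling.

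Section 6.6 handles a comparable situation differently. After a positive pregnancy test, further doses stop but the participant is encouraged to complete the other study procedures.

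**2. Draws at risk per participant**

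Post-baseline antibody draws (Protocol 6.2.1 and 6.2.2):

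- Cohort A: Days 15, 29, 43, 57, 119, 209, 299, 394 (8 draws).
- Cohort B: Days 15, 29, 91, 181, 271, 366 (6 draws).

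Post-baseline T-cell draws (Appendices 1 and 2):

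- Cohort A: Days 15, 29, 43, 57, 209, 394 (6 draws).
- Cohort B: Days 15, 29, 181, 366 (4 draws).

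Draws lost = number of scheduled days on or after the day from which safety-only visits apply, if they then run to the Final Visit as the sentence says.

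| Safety-only from participant day | A antibody | A T-cell | B antibody | B T-cell |
|---|---|---|---|---|
| 30 | 6 of 8 | 4 of 6 | 4 of 6 | 2 of 4 |
| 58 | 4 of 8 | 2 of 6 | 4 of 6 | 2 of 4 |
| 182 | 3 of 8 | 2 of 6 | 2 of 6 | 1 of 4 |

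In the Day 30 row, Cohort A assumes that the second dose was given on Day 29. The 6 antibody draws lost are then every draw after that dose.

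If sampling restarts when the pause is lifted, only draws falling due during the pause are lost. A pause covering Days 10 to 30 of a Cohort B participant would cost Days 15 and 29, which is 2 of 6. A pause covering no scheduled draw would cost none.

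Planned groups are small: 12/3 = 4 per arm in Sub-cohort A1, 24 × 3/4 = 18 and 24 × 1/4 = 6 in Sub-cohort A2, and 36/3 = 12 per arm in Cohort B.

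**3. Chance of a trigger (illustration only)**

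With an assumed probability p per participant and 72 independent participants, P(at least one) = 1 − (1 − p)^72.

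| Assumed p | P(at least one) |
|---|---|
| 0.1% | 7% |
| 0.5% | 30% |
| 1% | 52% |
| 2% | 77% |

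These are upper illustrations, because an event after the last dose in the study leaves no dosing to pause.

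**The case against.** The strongest reply is that the sentence should be read in context. A pause lasts only until the SRC has reviewed the data, the SRC may let the study continue unmodified, and section 4.2.4 foresees procedures resuming. The sentence also points to a Schedule of Assessments that includes the draws. On that reading normal sampling returns when the pause is lifted, and the sponsor may have meant safety-only follow-up for a permanent stop alone. This has weight. A reader might infer that one event, even if cleared by the SRC, ends immunogenicity measurement for good in both cohorts. The documents do not support that as a certainty, because the resumption text points the other way. What the reply cannot supply is a statement that sampling restarts, or any provision for fully dosed participants while a pause lasts.

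Three further points stand:

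- Safety-only follow-up after a permanent stop is a legitimate sponsor choice and is not in itself an error.
- Some Cohort A samples would be lost to the main analysis anyway. The Immunogenicity Analysis Set requires the specified doses within the predefined window, the Day 29 window is +1 day, and repeating summaries on the Full Analysis Set is optional (SAP 4.2 and 4.5.1). A second dose delayed by a pause may therefore remove a participant's later results regardless of sampling. The avoidable loss falls mainly on participants who have completed their assigned doses.
- Both primary objectives are descriptive, with no formal hypothesis test, so neither power nor type I error is affected.

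**Conclusion.** The point holds as a conflict in the written text. Section 4.2.4 does not separate a temporary pause from a permanent stop and does not exempt participants who have completed their doses. It cannot be reconciled with Primary Objective 2, section 7.5.4 or the schedule it cites. Sites would be left to choose between two instructions.

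Followed literally from participant Day 30, the rule costs 6 of 8 post-baseline antibody draws in Cohort A and 4 of 6 in Cohort B. This assumes that safety-only visits run to the Final Visit; if sampling resumes when the pause is lifted, the loss is limited to draws due during the pause. Samples taken before the pause remain usable.

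A reader might add up every scheduled post-dose draw, 8 × 36 + 6 × 36 = 504, and treat that as the expected loss. It is only a ceiling: it would need a pause before any post-dose draw, and Cohort B already had antibody data when Sub-cohort A2 was introduced (Protocol 3.1.1). Nor are the 7% to 77% figures estimates of the chance of a pause, since they rest entirely on assumed rates. The harm is lost data and precision for a primary objective in small groups.

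**What to change.** Reconcile the closing sentence of section 4.2.4 with the resumption text beside it and with Appendices 1 and 2. The amended text should state that:

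1. during a temporary pause, scheduled immunogenicity and T-cell sampling continues in vaccinated participants, at minimum in those who have completed their assigned doses;
2. the full Schedule of Assessments applies again once the pause is lifted;
3. safety-only follow-up, if the sponsor wants it, is limited to a permanent stop;
4. Cohort A visits timed from the second dose are handled in a defined way when that dose is delayed or not given.

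The SAP should add a short rule on how samples missed or displaced by a pause are reported.

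The change concerns data collection only. Pausing triggers, SRC review and dosing decisions are unchanged. The cost is a short protocol amendment and a line in the SAP, for sampling that the schedule already contains. The small downside is that participants continue to give blood for immunogenicity while dosing is suspended.
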